#### 11.1.6. PERCIST 1.0 Response [46]

Measurability of lesions at baseline: 1) Measurable target lesion is hottest single tumor lesion SUL of "maximal 1.2 cm diameter volume ROI in tumor" (SUL peak). SUL peak is at least 1.5 fold greater than liver SUL mean +2 SDs (in 3 cm spherical ROI in normal right lobe of liver). If liver is abnormal, primary tumor should have uptake > 2.0 x SUL mean of blood pool in 1 cm diameter ROI in descending thoracic aorta extended over 2 cm z axis. 2) Tumor with maximal SUL peak is assessed after treatment. Although typically this is in the same region of tumor as that with highest SUL peak at baseline, it need not be. 3) Uptake measurements should be made for peak and maximal single-voxel tumor SUL. Other SUV metrics, including SUL mean at 50% or 70% of SUV peak can be collected as exploratory data; TLG can be collected ideally on basis of voxels more intense than 2 SDs above liver mean SUL (see below). 4) These parameters can be recorded as exploratory data on up to 5 measureable target lesions, typically the 5 hottest lesions.

Normalization of uptake: Normal liver SUL must be within 20% (and <0.3 SUL mean units) for baseline and follow up study to be assessable. If liver is abnormal, blood-pool SUL must be within 20% (and <0.3 SUL mean units) for baseline and follow up study to be assessable. Uptake time of baseline and follow up study must be within 15 minutes of each other to be assessable. Same scanner or model at same site, injected dose, acquisition protocol and software should be used.

Complete Metabolic Response (CMR): Complete resolution of FDG uptake within measureable lesion so that it is less than mean liver activity and indistinguishable from surrounding background blood pool levels. Disappearance of all other lesions to background blood pool levels. No new FDG avid lesions.

Partial Metabolic Response (PMR): Reduction of minimum of 30% in target measureable tumor FDG SUL peak. Absolute drop must be at least 0.8 SUL units as well. Measurement is commonly in same lesion at baseline but can be another

lesion if that lesion was previously present and is the most active lesion after treatment. No new lesions.

Progressive Metabolic Disease (PMD): >30% increase in FDG SUL peak, with >0.8 SUL unit increase in tumor SUV peak from baseline scan in pattern typical of tumor and no of infection/treatment effect.

Stable Metabolic Disease (SMD): Not CMR, PMR or PDDATA REPORTING / REGULATORY CONSIDERATIONS

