### **1.3. Exploratory Objective(s)**

- To explore early FDG-PET and functional MRI changes to this combination and correlate to objective imaging response if feasible
- To evaluate changes in pharmacodynamic changes in pERK, pS6, pAKT, GLUT1 in blood and tumor tissue pre and post treatment in patients with easily accessible tumors
- To explore circulating tumor DNA, germline and tumor genomic alterations in patients with sporadic or NF1 associated MPNST
- To evaluate changes in immune infiltrates in blood and tumor tissue pre and post treatment

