#### **9.1.1. Mandatory**

9.1.1.1. Imaging FDG-PET will be obtained at baseline and on Cycle 1 Day 11 ( $\pm 3$ ) to assess for early FDG-PET response. If baseline FDG-PET is negative (avidity is not measureable), then second FDG-PET is not required.

Imaging: For patients who have MRI imaging done for tumor disease evaluation, DWI/ADC mapping sequence will be performed if feasible (mandatory if feasible) at baseline and at the time of disease evaluation. This sequence will add less than 3 minutes of scanning time and will explore the value of functional MRI imaging technology.

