#### 11.1.1. Definitions

Evaluable for PET response: Patient must have FDG-PET performed at time points stated in protocol to be evaluable for PET response. PET response will be measured by PERCIST 1.0 (see section 11.1.6).

Evaluable for objective response: Any patient who is enrolled and receives at least one dose of selumetinib and one dose sirolimus will be considered evaluable for response provided: (1) the patient demonstrates progressive disease or death while on protocol therapy; or (2) the patient is observed on protocol therapy for at least one cycle and the tumor is not removed surgically prior to the time complete response or partial response is confirmed; or (3) the patient demonstrates a complete or partial response or stable disease as confirmed according to protocol criteria. The evaluation period for determination of best response will be 6 treatment cycles. All other patients will be considered non-responders.

Evaluable for toxicity: All patients who receive at least one dose of selumetinib or sirolimus and either experience a toxicity or complete the first cycle with no toxicity will be considered in the evaluation of toxicity.

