#### 11.1.4. Response Criteria

**Complete Response (CR):** Disappearance of all target and non-target lesions. Any pathological lymph nodes whether target or non-target must have reduction in short axis to <10mm.

**Partial Response (PR):** A > 30% decrease in the sum of the diameters of target lesion, taking as reference the baseline sum diameters.

**Progressive Disease (PD):** At least a 20% increase in the sum of the target lesions, taking reference the smallest sum on study (this includes baseline if that is the smallest on study). In addition to the relative increase in 20%, the sum must also demonstrate an absolute increase of at least 5mm. The appearance of one or more new lesions is also considered progression. In the presence of SD or PR in the target disease, but unequivocal progression in non-target or non-measurable disease, the patient has PD if there is an overall level of substantial worsening in non-target disease such that the overall tumor burden has increased sufficiently to merit discontinuation of therapy.

**Stable Disease (SD):** Neither sufficient shrinkage to qualify for PR nor sufficient increase to qualify for PD, taking as reference the smallest sum diameters while on study.

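### Section 11.1.6 bars new FDG-avid lesions from CMR and PMR but leaves them out of PMD, so such a patient is filed as metabolically stable unless the hottest SUL peak also crosses the PMD threshold

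*Combined protocol and SAP*

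**What the plan says.** Section 11.1.1 sends the reader to 11.1.6 for the PET criteria: "PET response will be measured by PERCIST 1.0 (see section 11.1.6". Section 11.1.6 then writes out four categories.

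- **CMR** carries the condition "No new FDG avid lesions".
- **PMR** needs a fall of at least 30% and at least 0.8 SUL units. It may be measured in a different "lesion if that lesion was previously present and is the most active lesion after treatment. No new lesions".
- **PMD** reads "Progressive Metabolic Disease (PMD): >30% increase in FDG SUL peak, with >0.8 SUL unit increase in tumor SUV peak from baseline scan". The rest of that sentence asks only that the pattern look like tumor rather than infection or treatment effect.
- **SMD** is whatever is left after CMR, PMR and PD. The abbreviation used there is PD, not PMD.

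The same section says which lesion is measured at follow-up: "Tumor with maximal SUL peak is assessed after treatment". It adds that this need not be the region that was hottest at baseline.

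For CT/MRI, section 11.1.4 says "The appearance of one or more new lesions is also considered progression", and its best-response table makes any new lesion PD.

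The scans are mandatory. According to 9.1.1, "FDG-PET will be obtained at baseline and on Cycle 1 Day 11", within 3 days either way. Their use is exploratory (1.3): "To explore early FDG-PET and functional MRI changes to this combination and correlate to objective imaging response if feasible".

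**The concern.** New lesions are named twice as disqualifying, and for PMR even the substitute lesion must have been there before. No category then receives the patients who are disqualified. Because SMD is defined by exclusion, it collects them by default, and spread to a new site is recorded as metabolic stability.

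At stake is how clean the SMD and PMD groups are when early PET is related to later imaging response. If patients with new avid lesions sit among the stable ones, the stable group is mixed and the contrast between the two non-responder groups is blurred. In a trial of at most 21 patients, a few such cases can change how the table reads.

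**Working it through.** No figure in the plan depends on this rule, so there is none to reproduce. The check is to apply the four definitions as a decision rule.

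**Inputs from 11.1.6.** PMR: change of −30% or lower, a fall of at least 0.8 units, and no new lesion. PMD: change above +30% and a rise above 0.8 units. SMD: the rest, reading PD as PMD.

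**Assumed inputs.** Baseline SUL peaks of 2.5, 5 and 8, for illustration only. The patients shown do not meet CMR.

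**Thresholds for PMD.** The follow-up peak must exceed both 1.3 × baseline and baseline + 0.8.

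- Baseline 2.5: 1.3 × 2.5 = 3.25 and 2.5 + 0.8 = 3.3, so the peak must exceed 3.3 (a rise above 32%).
- Baseline 5: 6.5 and 5.8, so the peak must exceed 6.5.
- Baseline 8: 10.4 and 8.8, so the peak must exceed 10.4.

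**Result.**

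| Change in hottest SUL peak | No new lesion | New lesion, as written | New lesion, with a new-lesion criterion in PMD |
|---|---|---|---|
| −50% | PMR | SMD | PMD |
| −31% | PMR at 5 and 8; SMD at 2.5 (fall 0.775, below 0.8) | SMD | PMD |
| −10%, 0, +10%, +29% | SMD | SMD | PMD |
| +33%, +50% | PMD | PMD | PMD |

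As written, every new-lesion case from −50% to +29% is SMD. At +33% and above the patient is PMD because of the uptake, not because of the new lesion.

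**A new lesion that is itself the hottest.** Take a baseline peak of 5. A new lesion with peak 7 gives (7 − 5)/5 = +40% and +2.0 units, so PMD. A new lesion with peak 6 gives +20% and +1.0 unit, so SMD as written.

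**What does not move.** New lesions bar CMR and PMR under either wording, so the responder group is identical. Section 11.1 evaluates response and progression by RECIST 1.1, and PET class is not an input to the clinical benefit rate, the Simon boundaries or PFS in section 13.1.

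**Weight of one patient.** 1/21 = 4.8 percentage points if all 21 have an evaluable pair of scans; 1/7 = 14.3 points if the trial stops after stage 1 and all 7 do.

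**The case against.** **The protocol adopts a published standard.** Sections 2.5.1 and 11.1.1 cite PERCIST, and the source may have its own rule for new lesions. That cannot be checked from the documents. It does not close the gap: 11.1.1 points to 11.1.6, which writes the criteria out without such a rule. If the source differs, PET readers have two rules to choose between.

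**A hot new lesion can trigger PMD by itself.** This is correct, because the hottest tumor at follow-up is the one assessed. It is why the conclusion carries a condition. It does not help a new lesion whose uptake stays at or below the threshold.

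**SMD says PD, not PMD.** If PD means RECIST progression as in 11.1.4, a patient so classed is not SMD. Below the uptake threshold the patient is not PMD either, and so has no PET category. In the text available for review the SMD line runs into the next heading, so a reading fault in that abbreviation is possible. The omission from PMD does not depend on it.

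**The consequence is small.** This stands. The objective is exploratory and to be met only if feasible. Section 13.4 plans descriptive summaries and paired-type comparisons of changes in FDG avidity, which do not use the PMD label. No rate of early metabolic failure is planned.

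**CT/MRI and PET are different measurements.** A reader might infer that the patients misfiled as stable are RECIST progressors by definition. The documents do not support that: 11.1.4 governs CT/MRI, first repeated before cycle 3, and a focus seen only on the Day 11 PET need not be visible there.

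**Conclusion.** The point holds as a drafting error in an exploratory definition. Applied as written, 11.1.6 calls a patient with a new FDG-avid lesion stable, or gives no category if PD means RECIST progression, unless the hottest SUL peak also rises by more than 30% and more than 0.8 units. This conflicts with how the protocol treats new lesions in 11.1.4. Only the SMD/PMD split is affected.

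A reader might try to turn the rapid progression described in section 2.1.3 into a number of misfiled patients. The documents do not support a count. Table 1 gives PFS from a median of 1.7 months to 13 weeks. Nothing states the share of progressions that appear as new lesions, how RECIST progression relates to change visible on PET at Day 11, or the actual interval between the two scans. Some new-lesion patients would be PMD anyway, and those with a negative baseline PET need no second scan (9.1.1.1).

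A reader might also infer that growth in the extent of uptake should count as PMD. The documents give no basis for that, and it is not part of this point.

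**What to change.** Amend two definitions in 11.1.6 before PET categories are analysed:

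- PMD: a rise in SUL peak of more than 30% and more than 0.8 units, **or** any new FDG-avid lesion, in either case with a pattern typical of tumor and not explained by infection or treatment effect.
- SMD: not CMR, PMR or **PMD**.

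The cost is about a sentence of protocol wording. It needs no extra scans, readers or patients, and changes no sample size or decision rule. Fixing the wording first matters because settling how to class new lesions after seeing the results would weaken any reported link between early PET and imaging response.

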## **12. DATA REPORTING / REGULATORY CONSIDERATIONS**

### **12.1. Method**

A final study report describing the outcome of the trial will be created at the end of the study.

### **12.2. Data, Safety and Monitoring**

SARC is responsible for overseeing the conduct of this trial which includes review of data, safety and monitoring for this trial. SARC Clinical Trials Review Committee convenes monthly and will provide safety oversight for this trial. The purpose of the Clinical Trials Review Committee is to review the status of the ongoing SARC studies, which includes, but is not limited to:

- Review of all safety data (Serious Adverse Events reported)
- Review of protocol deviations/violations
- Review of study progress/accrual
- Discussion of statistical aspects of all protocols

The committee is chaired by the SARC Medical Officer, who is responsible for leading the meeting and providing medical oversight. Attendance includes all Principal Investigators on active SARC studies, SARC Research Project Managers, SARC President, and a biostatistician.

Safety oversight for this trial is also supported by the SARC Clinical Research Committee which is made up of senior sarcoma investigators and the SARC President and Chief Executive Officer. This committee is provided with the clinical trial review committee minutes monthly for their review, and also convenes quarterly. The medical officer updates the committee on the ongoing clinical trial status as well as any areas of concern particularly related to safety. This committee provides an additional level of medical oversight for this trial.

The SARC Medical Officer will also be the Medical monitor for this study.

The medical monitor is required to review all unanticipated problems involving risk to subjects or others, serious adverse events and all subject deaths associated with the protocol and provide an unbiased written report of the event. At a minimum, the Medical monitor must comment on the outcomes of the event or

problem, and in the case of a serious adverse event or death, comment on the relationship to participation in the study. The Medical monitor must also indicate whether he/she concurs with the details of the report provided by the principal investigator. Reports for events determined by either the investigator or medical monitor to be related to participation and reports of events resulting in death must be promptly forwarded to the sponsor. SARC will be responsible for forwarding reports to the SARC medical officer.

The SARC Medical Officer will also function as the Department of Defense (DoD) required “Independent Research Monitor”. The DoD Independent Research Monitor will be responsible evaluating any risks or concerns of the research in addition to overseeing the safety of the research and reporting observations/findings to the IRB of Record or a designated official. The DoD Independent Research Monitor will review all unanticipated problems involving risk to volunteers or others associated with the protocol and provide an unbiased written report of the event to the IRB of Record. The DoD Independent Research Monitor may discuss the research protocol with the investigators, interview human subjects, and consult with others outside of the study about the research. The DoD Independent Research Monitor shall have authority to stop the research protocol in progress, remove individual human subjects from the study, and take whatever steps are necessary to protect the safety and well-being of human subjects until the IRB can assess the monitor’s report. The DoD Independent Research Monitor is responsible for promptly reporting their observations and findings to the IRB.

DoD Independent Research Monitor functions may include:

- Observing recruitment and enrollment procedures and the consent process for individuals, groups or units,
- Overseeing study interventions and interactions,
- Reviewing monitoring plans and UPIRTSO reports;
- Overseeing data matching, data collection, and analysis

At a minimum, the DoD Independent Research Monitor:

- May discuss the research protocol with the investigators, interview human subjects, and consult with others outside of the study about the research;
- Shall have authority to stop a research protocol in progress, remove individual human subjects from a research protocol, and take whatever steps are necessary to protect the safety and well-being of human subjects until the IRB can assess the monitor’s report;
- Shall have the responsibility to promptly report their observations and findings to the IRB or other designated official and the HRPO.

Sites with patients on study will be monitored at least once during the duration of the study. Selected patient charts as well as the participating institution’s Standard Operating Procedures may be monitored at the time of the visit. Data from participating institutions should be available when the protocol is monitored.

The institutional principal investigator is responsible for having all records and data for all patients enrolled at his/her institution available at that institution for monitoring.

Participating study sites will be informed of findings on a regular basis and be provided with ample information to report to their local IRB in accordance with local site policies.

The knowledge of any pending compliance inspection/visit by the FDA, OHRP, or other government agency concerning clinical investigation or research, the issuance of Inspection Reports, FDA Form 483, warning letters or actions taken by any Regulatory Agencies including legal or medical actions and any instances of serious or continuing noncompliance with the regulations or requirements will be reported immediately to USAMRMC ORP HRPO.

### **12.3. Patient Accrual and Participating Centers**

The study would be conducted through the SARC consortium in collaboration of the NF Consortium with 10-15 consortium centers.

### **12.4. Multi-institutional Guidelines**

The trial coordinating center (Operations Center) will be SARC. Patients will be registered electronically via the study website, and adverse events (as defined in Section 7) will be reported to the operations center.

#### IRB Approvals

SARC will be the Operations Center. The protocol must be approved at the treating institution prior to enrolling patients. Documentation of individual institutional IRB approval, for the current protocol must be provided to the SARC Operations Office prior to enrolling patients on the trial. They may be provided via e-mail, fax, or US Mail. In addition, documentation of approval of all protocol amendments and of yearly continuing review must be provided to the SARC Operations Office Research Project Manager to allow patient entry. The mailing address is:

SARC  
[name]  
[name]  
[contact]  
[contact]  
Email: [name]

#### USAMRMC HRPO Approvals

As this trial receives funding by the Department of Defense, approval of the protocol must be obtained from the USAMRMC ORP HRPO in addition to the institutional IRB prior to implementation. Documentation of individual institutional IRB approval, for the current protocol must be provided to SARC at the Operations Center prior to enrolling patients on the trial. In addition,

documentation of approval of all protocol amendments and of yearly continuing review must be provided to the Operations Center to allow patient entry. They may be submitted via e-mail, fax, or US Mail. SARC will submit these documents to the USAMRMC Office of Research Protections (ORP), Human Research Protections Office (HRPO).

Major modifications to the research protocol and any modifications that could potentially increase risk to subjects must be submitted to the USAMRMC ORP HRPO for approval prior to implementation. All other amendments will be submitted with the continuing review report to the USAMRMC ORP HRPO for acceptance. A copy of the approved continuing review report and the local IRB approval notification will be submitted to the USAMRMC ORP HRPO as soon as these documents become available. A copy of the approved final study report and local IRB approval notification will be submitted to the USAMRMC ORP HRPO as soon as these documents become available.

#### Amendments and Consents

SARC will be the Operations Center. IRB approval of the current protocol, protocol amendments, and yearly continuing review must be provided to the SARC Operations Office. In addition, a copy of the currently approved informed consent of each participating site will be kept on file at SARC. SARC will submit these documents to the USAMRMC ORP HRPO.

#### Patient Registration

Patient Registration will be centrally managed by the Operations Center electronically via the study website.

#### Data Collection and Toxicity Reporting

Registration reports will be generated by the Operations Center to monitor patient accruals and completeness of registration data. Routine data quality reports will be generated to assess missing data and inconsistencies by the study coordinator. Any potential problems will be brought to the attention of the Principal Investigator for discussion and action.

Access to the password protected study database will be limited to individuals involved in the clinical trial: SARC, Study PI, participating site PIs, and research nurses and data managers responsible for this trial.

Shipment and receipt of specimens and imaging studies sent for correlative studies will be entered on the study website and can thus be tracked.

A monthly phone conference will be held on an as needed basis between the Principal Investigator, the Operations Center, associate investigators, and participating sites to address QA issues, accrual, observed toxicities, and compliance with submission of required studies.

## **13. STATISTICAL CONSIDERATIONS**

### **13.1. Study Design/Endpoints**

The primary endpoint will be clinical benefit rate, which will be defined as a CR, PR, or stable disease  $\geq 4$  cycles. An evaluable patient will be classified as a responder (success) for the primary endpoint if the patient achieves a partial response (PR), complete response (CR), or stable disease (SD) at  $\geq 4$  cycles. The target clinical benefit rate will be 30% ( $p_1=0.30$ ), and a clinical benefit rate  $\leq 5\%$  ( $p_0=0.05$ ) will be considered uninteresting. Using a Simon's optimal two-stage phase II design with an  $\alpha=0.10$  (probability of accepting a poor treatment), and  $\beta=0.10$  (probability of rejecting a good treatment=0.10; power= 90%). Stage 1 will require 7 patients, with no further accrual if 0 of 7 respond. Since it may take several months to determine if a patient has responded, accrual may be temporarily paused while waiting to determine if there is at least one patient with a response among the 7 evaluable patients enrolled on stage 1. If  $\geq 1/7$  patients respond, accrual will continue until 21 patients have been enrolled. If  $\geq 3/21$  patients respond, this combination will be considered of sufficient activity, while 1-2 of 21 with benefit would be insufficient. Under the null hypothesis ( $p_0=0.05$ ), the expected sample size would be 11.2 patients, and the probability of early termination would be 69.8%.

Progression-Free Survival (PFS) is defined as the duration of time from the start of treatment to the time of objective progression or death.

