## **Efficacy Evaluations**

- Response evaluation (RECIST) with appropriate imaging studies (MRI/CT) will be performed at baseline, prior to cycles 3, 5, 7 and then every 3 cycles (prior to cycles 10, 13, 16, etc.).

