## 5.5. Criteria for Removal off Protocol Therapy

Treatment may continue until one of the following criteria applies:

- Progressive Disease
  - Patients with radiographic or clinical evidence of disease progression following any treatment cycle will discontinue protocol therapy.
- Toxicity
  - Adverse events requiring removal from therapy.
  - Patient has not met parameter to start subsequent cycle.
- Administrative
  - Patient refusal of further treatments. Reasons must be noted on the patient's record.
  - If deemed in the best interest of the patient to be taken off protocol therapy, the Principal Investigator should be notified and the reasons for withdrawal noted in the patient's medical record.
  - Serious protocol violation as determined by the Principal Investigator
  -
- Another Medical
  - Development of any concurrent medical condition that precludes further administration of therapy.

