## 5.6. Duration of Follow Up

Patients will be followed for adverse event(s) until 30 days after last treatment or until resolution or stabilization of the adverse event (whichever comes last). Patients who are removed from protocol therapy for a reason other than disease progression, should be followed up every 6 months by imaging to monitor disease status. Every effort should be made to collect information regarding disease status until the start of new anti-cancer therapy, disease progression, or death. Once a patient experiences confirmed disease progression or starts a new anti-cancer therapy, the patient should be contacted by telephone every 6 months to assess for survival status until death or withdrawal of consent or end of study, whichever occurs first.

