## 5.7. Criteria for Removal from Study

Patients will be removed from study when any of the criteria listed below applies. The reason for study removal and the date the patient was removed must be documented in the Case Report Form including death or lost to follow up.

- Patient or guardian withdrawal of consent. Reasons must be noted on the patient's record.
- Death

- Lost to follow up
- Enrollment onto another SARC treatment study or SARC long term follow up study.

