#### 7.1.1.6. Progression of Underlying Malignancy

Progression of underlying malignancy is not reported as an adverse event if it is clearly consistent with the suspected progression of the underlying cancer as defined by RECIST criteria, or other criteria as determined by protocol.

**Hospitalization due solely to the progression of underlying malignancy should NOT be reported as a serious adverse event.** Clinical symptoms of progression may be reported as adverse events if the symptom cannot be determined as exclusively due to the progression of the underlying malignancy, or does not fit the expected pattern of progression for the disease under study.

Symptomatic deterioration may occur in some patients. In this situation, progression is evident in the patient's clinical symptoms, but is not supported by the tumor measurements. Or, the disease progression is so evident that the investigator may elect not to perform further disease assessments. In such cases, the determination of clinical progression is based on symptomatic deterioration. These determinations should be a rare exception as every effort should be made to document the objective progression of underlying malignancy.

If there is any uncertainty about an adverse event being due only to the disease under study, it should be reported as an AE or SAE.

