## 11. MEASUREMENT OF EFFECT

### 11.1. Antitumor Effect – Solid Tumors

For the purposes of this study, patients should be re-evaluated for response prior to every odd cycle.

Response and progression will be evaluated in this study using the new international criteria proposed by the revised Response Evaluation Criteria in Solid Tumors (RECIST) guideline (version 1.1) [65]. Changes in the largest diameter (unidimensional measurement) of the tumor lesions and the shortest diameter in the case of malignant lymph nodes are used in the RECIST criteria.

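### PFS is likely overstated because clinical progression is not an event and off-therapy scans are 6 months apart; sections 5.6 and 5.7 conflict on survival follow-up, which puts OS at risk of informative censoring

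*Combined protocol and SAP*

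**What the plan says.** **PFS event.** Section 13.1: PFS "is defined as the duration of time from the start of treatment to the time of objective progression or death". Section 13.4 plans Kaplan-Meier estimates, with 6 and 12 months as example landmarks. It gives no censoring rule.

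**Stopping therapy.** Section 5.5: "Patients with radiographic or clinical evidence of disease progression following any treatment cycle will discontinue protocol therapy". Section 7.1.1.6 recognises progression that tumour measurements do not support, or that is so evident that the investigator forgoes further assessment. In such cases "the determination of clinical progression is based on symptomatic deterioration".

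**Imaging after therapy.** The End of Therapy list in 10.2 contains no imaging, and the end-of-therapy column of the Study Calendar has no tumour evaluation. Under 5.6, patients who stop for a reason other than progression "should be followed up every 6 months by imaging to monitor disease status". After confirmed progression or new anti-cancer therapy, 5.6 provides telephone contact for survival every 6 months.

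**Imaging on therapy.** The synopsis schedules scans "prior to cycles 3, 5, 7 and then every 3 cycles (prior to cycles 10, 13, 16, etc"; sections 2.4.1 and 10.2 and the Study Calendar agree. Section 11.1 says that "patients should be re-evaluated for response prior to every odd cycle".

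**Survival follow-up.** Section 5.6 continues contact until the patient dies, withdraws consent or the study ends. Section 5.7 lists, as a reason for removal from the study, "Enrollment onto another SARC treatment study or SARC long term follow up study". OS is a secondary objective (1.2), but section 13 gives it no definition, method or censoring rule.

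**The concern.** PFS is a secondary efficacy endpoint of a single-arm trial, so no control arm shares a detection bias. Any reading of PFS against earlier trials, such as the median of 1.7 months for sorafenib in Table 1, absorbs all of it. Section 2.1.3 describes a disease with a median time to progression under 2 months. An off-therapy scan interval of 6 months is three times that, and as long as the first landmark named in 13.4.

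The patients affected are those who fail treatment by clinical decline or by intolerance. If their progression is recorded late or never, the PFS curve looks better because of how they were observed.

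For OS, the two follow-up sections cannot both be carried out for a patient who joins another SARC study. If 5.7 prevails, survival data are lost for a group whose prognosis may differ from that of the rest.

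**Working it through.** **1. The plan's own figures.** No figure is stated for PFS or OS. The two-stage design does reproduce. The probability of early termination under p0 is 0.95^7 = 0.698 (stated 69.8%), and the expected sample size is 7 + (1 − 0.698) × 14 = 11.2 (stated 11.2). Exact power at 30% is 0.904, and exact type I error is 0.064 against the 0.10 limit. None of these uses PFS or OS.

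**2. Clinical progression.** Therapy stops (5.5). No scan is required at end of therapy (10.2, Study Calendar). The 6-monthly imaging in 5.6 is for patients who stopped for other reasons. Such a patient has no scheduled route to an objective event before death. With no censoring rule, the analyst either carries the patient to death or censors at the last scan. Both omit an event that has occurred.

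**3. Scan interval.** Scans before cycles 3, 5 and 7 fall at about weeks 8, 16 and 24. A patient who stops for toxicity at week 6 has had no on-study scan. The next scheduled scan is at week 6 + 26 = 32, after the 6-month point (week 26). Progression in between is counted by then only through death or an unscheduled scan.

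**4. Size for PFS, by simulation.** There were 200,000 simulated patients per scenario. Assumptions that are not in the documents: exponential times; median 6 months from progression to death; a stated share assigned a non-progression stop, uniform over months 0 to 4, which takes effect only if it precedes progression; no new therapy and no unscheduled scans. The reference counts clinical progression on its date and keeps everyone on the on-therapy calendar. Where a range is given, it spans two runs: clinical progression censored at the last scan, or carried to death.

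| True median (months) | Clinical progression / assigned stop | Reference 6-month PFS | As written | Shift (points) |
|---|---|---|---|---|
| 1.7 | 0% / 20% | 10.4–10.5% | 15.8–16.0% | 5.4–5.5 |
| 1.7 | 10% / 0% | 10.3–10.4% | 11.8–16.0% | 1.4–5.7 |
| 1.7 | 10% / 20% | 10.4% | 17.7–21.0% | 7.3–10.6 |
| 1.7 | 20% / 30% | 10.2% | 22.9–28.3% | 12.7–18.1 |
| 3.0 | 0% / 20% | 27.8–27.9% | 33.3–33.4% | 5.5 |
| 3.0 | 10% / 0% | 27.5–27.6% | 30.4–32.6% | 2.8–5.1 |
| 3.0 | 10% / 20% | 27.5–27.7% | 35.9–37.6% | 8.4–9.9 |
| 3.0 | 20% / 30% | 27.4–27.5% | 41.7–43.9% | 14.3–16.4 |
| 6.0 | 0% / 20% | 52.8% | 56.8–56.9% | 4.0–4.1 |
| 6.0 | 10% / 0% | 52.6% | 55.8–56.0% | 3.2–3.4 |
| 6.0 | 10% / 20% | 52.6% | 59.5–59.6% | 6.9–7.0 |
| 6.0 | 20% / 30% | 52.1–52.3% | 63.9–64.1% | 11.8 |

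Hand check of the reference: the last scan before 6 months is at 6 × 28 / 30.4375 = 5.52 months. At a median of 3 months, 0.5^(5.52/3) = 0.279, which agrees. The median often does not move, because it sits on a scan date.

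**5. Size for OS, by simulation.** Assumptions: median OS 10 months; 10%, 20% or 30% of patients enter another study and are censored between months 1 and 6.
- Entrants at half the hazard: true 12-month OS of 45.8–50.2% is estimated as 44.1–45.4%, a shift of −1.7 to −4.8 points.
- Equal hazard: no bias.
- Entrants at 1.5 times the hazard: 39.0–42.0% is estimated as 41.8–42.9%, a shift of +0.9 to +2.8 points.

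**6. On-therapy interval.** Odd cycles (11.1) mean scans before cycles 3, 5, 7, 9, 11 and 13. The calendar gives 3, 5, 7, 10 and 13. They agree to week 24 and then differ, at 8 against 12 weeks between scans. This hardly touches 6-month PFS.

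**The case against.** Objective progression or death is a recognised PFS definition, and making investigator-judged progression a main event in an uncontrolled trial would be a trade-off. That stands, and the main definition should stay.

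Section 7.1.1.6 limits the first mechanism: "These determinations should be a rare exception as every effort should be made to document the objective progression of underlying malignancy". Section 5.6 asks for every effort to collect disease status until new therapy, progression or death, and 10.3 lists imaging, if feasible, at removal from the study. These reduce the bias but do not remove it. They assign no event date or analysis rule, and 10.3 applies at removal from the study, not at the end of therapy.

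Three stronger readings are tempting.
- A reader might infer that a patient who stops at week 6 must count as progression-free at 6 months. That does not hold: death is an event, and an unscheduled scan may document progression.
- A reader might divide by 21 and infer that 2 to 4 such patients add 2/21 to 4/21, or 9.5 to 19.0 points. That assumes each would otherwise have had an event by 6 months and that none dies or is scanned first. In the simulation, with 20% assigned an early stop (about 4 of 21), the scan interval alone adds about 4 to 6 points.
- A reader might infer that OS is informatively censored in a known direction. The documents contain no OS censoring rule, 5.6 does not list entry to another study as an end of contact, and the simulated shift takes either sign or zero. Transfer to a SARC long-term follow-up study need not lose data if the records are linked.

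**Conclusion.** The point stands as a should-fix. PFS is likely biased upward, because both mechanisms act in that direction. The amount cannot be fixed from the documents, which give neither the frequency of clinical progression nor that of stopping without progression. The simulated shift in 6-month PFS of about 1 to 18 points is an illustration that rests on the assumed frequencies and exponential times; the upper end needs 20% undocumented clinical progression together with 30% assigned an early stop.

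For OS the finding is narrower: 5.6 and 5.7 conflict, and informative censoring is a risk if 5.7 is followed. The illustrated shift at 12 months is about −5 to +3 points, and zero if entry to another study is unrelated to prognosis.

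The conflict in the on-therapy scan interval is real, but it is a matter of wording with little effect on 6-month PFS. PFS and OS carry no power calculation or decision rule, so the go/no-go decision is untouched.

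**What to change.** 1. **Section 13.4, PFS.** Keep objective progression or death as the main analysis. Add a sensitivity analysis in which clinical progression recorded as the reason for stopping (5.5) is an event on that date. Add a second one for patients assessed off the on-treatment calendar, for example interval-censored, or with progression dated at the next missed on-treatment scan. Do not simply censor at the last on-calendar scan: the week-6 patient would be censored at baseline, and later deaths would be thrown away.
2. **Section 5.7, OS.** State that entry to another SARC study does not end survival follow-up, and obtain vital status through the consortium, so that 5.7 agrees with 5.6. A line in 13.4 defining OS and its censoring should go with this.
3. **Section 11.1.** Reconcile the scan interval with the synopsis, 2.4.1, 10.2 and the Study Calendar.

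The cost is protocol wording, a recorded reason and date for stopping, and a little more analysis. No extra scans and no change in sample size are needed. The downside is a PFS figure that may look less favourable.
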